- **Physician-reported measures:** Systemic Lupus Erythematosus Disease Activity Index (SLEDAI), Physician's Global Assessment, LFA-REAL
- **Routine Lupus Labs:** CBC with differential, creatinine, C3 and C4, anti-dsDNA antibody, C-reactive protein, sedimentation rate, complete urinalysis, and urine protein:creatinine

Data Analysis: Robust cluster analysis. [name] will expand on our preliminary cluster analysis using latent profile analysis to include detailed patient-, physician- and laboratory measures. **Power Calculation:** In order to identify 4 clusters using 8 predictive variables, a minimum sample size of 320 patients is needed. If the cluster analysis identifies 7 distinct clusters, there will be sufficient power to include 5 predictive variables in the model with 350 patients. Differences in phenotypes across clusters, including patients' demographic, SLE history, patient- and physician-reported measures, and laboratory tests will be estimated by ANOVA and Chi-squared test.

Using our new knowledge about the quantitative differences in SLAQ responses by cluster, the qualitative information about symptoms from patient interviews, and clinical expertise, we will revise the SLAQ and create a new scoring system with individual Type 1 and 2 SLE scores. This new scoring system will be tested using 800 patient visits to determine if the new Type 1 and 2 SLE scores correspond to cluster assignment. Using logistic regression models, [name] will compare three commonly used physician-reported SLE measures, the SELENA-SLEDAI, physician's global assessment, and LFA-REAL™ to determine if model fit improves with physician-reported measures. Goodness of fit will be assessed by the Hosmer-Lemeshow chi-square test, and model discrimination will be assessed using C statistics to estimate the area under the receiver operating characteristic curve. To account for patients potentially contributing more than one visit to this analysis, generalized estimating equations (GEE) will be used.

Inclusion: Patients who are enrolled in the Duke Lupus Registry and gave informed consent through the Duke Lupus Registry (DLR) (IRB Pro00008875) and Sub-studies of the DLR (IRB Pro00094645).

Compensation: Data collected from patients enrolled in the Duke Lupus Registry will be retrospectively analyzed. No compensation will be provided as part of this analysis.

Aim 3. Conduct a pilot implementation study of the Type 1 and 2 SLE model into clinical care.

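### Aim 2 asks whether adding a physician measure improves model fit, but the only tool it assigns to fit, Hosmer-Lemeshow, checks one model's calibration and does not compare models

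*Combined protocol and SAP*

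**What the plan says.** All of this is in the combined protocol and SAP, Methods, Aim 2, Data Analysis.

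- The new scores are tested first: "This new scoring system will be tested using 800 patient visits". The stated aim of that step is "to determine if the new Type 1 and 2 SLE scores correspond to cluster assignment".
- Logistic models then compare three physician measures ("the SELENA-SLEDAI, physician's global assessment, and LFA-REAL™"), and the purpose is "to determine if model fit improves with physician-reported measures".
- The tools come in the next sentence: "Goodness of fit will be assessed by the Hosmer-Lemeshow chi-square test, and model discrimination will be assessed using C statistics". Fit is thus assigned to Hosmer-Lemeshow, and discrimination separately to C.
- Repeat visits are handled as follows: "To account for patients potentially contributing more than one visit to this analysis, generalized estimating equations (GEE) will be used".

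The document names no test of the added measure, no information criterion, and no interval, test or threshold for a difference in C between models. It gives no alpha, effect size or power for this step.

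**The concern.** The question is about two models: the new scores alone, and the new scores plus a physician measure. The tool assigned to fit looks at one model at a time. It asks whether predicted risks match observed frequencies across risk groups, and a model can pass while leaving out a powerful predictor. Two non-significant Hosmer-Lemeshow results could then be reported as no improvement in fit, although neither result bears on improvement. A change in the statistic from one model to the other is no better a guide, because it can move either way when a useful term enters.

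At stake is what the study can say about whether physician measures add to the new patient-reported scores. That is of real interest for a measure meant to be short and quick to use.

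**Working it through.** **No figure to reproduce.** The plan attaches no number to this comparison. The 320 and 350 patients quoted nearby belong to the cluster analysis (10 × 4 × 8 = 320; 10 × 7 × 5 = 350) and do not bear on it.

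**Why the test is blind here.** With g = 1…10 risk groups,

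HL = Σ (O_g − E_g)² / [n_g p̄_g (1 − p̄_g)], referred to chi-square on 10 − 2 = 8 df.

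Suppose the true model is logit P(Y=1) = a + b·x + c·w and w is omitted. The base model then estimates P(Y=1 | x), the average over w. If w is roughly linear in x, that average is close to a logistic curve in x with a different slope. Observed and expected counts agree, and HL rejects at about alpha. The miss rate is therefore about 1 − 0.05 = 0.95, which follows from the assumed alpha.

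**Inputs.** From the plan: 800 visits, a logistic model, physician measures considered against the new scores, repeat visits possible. Assumed, because the plan does not say: alpha 0.05; 10 HL groups; a binary outcome, about 30% in most runs; one base score with log-odds 1.0 per SD (odds ratio 2.7); one added measure with odds ratio 1.5 to 5 per SD; correlation 0 to 0.5 with the base score. There were 1,000 to 1,500 runs per scenario.

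**800 independent visits** (ranges over correlation 0, 0.3, 0.5; C at correlation 0.3; the odds ratio 1 row at correlation 0 only):

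| Added OR per SD | HL rejects base model | HL p-value larger in full model | C, base → full | Likelihood-ratio test detects |
|---|---|---|---|---|
| 1 (useless) | 4.5% | 49.1% | 0.742 → 0.743 | 4.5% |
| 1.5 | 4.6–5.5% | 49.2–51.6% | 0.757 → 0.773 | 98.3–99.7% |
| 2 | 4.6–5.5% | 46.9–51.3% | 0.762 → 0.801 | 100% |
| 3 | 4.2–4.9% | 49.2–51.1% | 0.762 → 0.839 | 100% |
| 5 | 4.6–5.8% | 50.6–52.5% | 0.756 → 0.876 | 100% |

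The HL columns do not separate a useless measure from a very strong one. The Monte Carlo standard error at 5% with 1,000 runs is √(0.05 × 0.95 / 1,000) = 0.7 percentage points, so these HL rejection rates are compatible with 5%.

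**Repeat visits.** A likelihood-ratio test is not directly available under GEE, so the relevant comparator is a patient-clustered robust Wald test. The ranges cover 400 patients × 2 visits and 200 × 4, with random-intercept SD 0, 1, 2 and correlation 0.3:

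| Added OR per SD | HL rejects base model | Clustered Wald detects | Mean rise in C |
|---|---|---|---|
| 1 (useless) | 4.3–7.4% | 4.0–5.9% | 0.001–0.002 |
| 1.5 | 3.6–8.2% | 65.7–98.8% | 0.012–0.016 |
| 2 | 4.7–5.6% | 98.4–100% | 0.028–0.039 |
| 3 | 4.5–6.1% | 100% | 0.056–0.076 |

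The two highest HL rates, 7.4% and 8.2%, come from the same setting (200 × 4, SD 2). One of them has a useless measure, so the excess is not a response to the omitted predictor.

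**Sensitivity.** With a skewed measure, HL rejected the base model in 3.3–5.1% of runs. At 320 visits the figure was 4.3–5.3%. The exception is a measure that is a quadratic function of the base score: HL then rejected in 99.8% of runs, because the included term had the wrong shape.

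**The case against.** The strongest reply is that the same sentence names two criteria. Pairing calibration with discrimination is conventional, and the question about fit can be read as covering both. C does respond. In 400 simulated runs at 800 independent visits (base odds ratio 2.7, correlation 0.4), it rose by more than 0.01 in 73%, 100% and 100% of runs at added odds ratios 1.5, 2.0 and 2.7, and in 0% when the measure was useless. This stands, and it limits the point. A reader might infer that the plan as a whole would miss a strong added predictor about 95% of the time. The documents do not support that: the figure describes Hosmer-Lemeshow alone, at an assumed alpha, and the plan never says that a change from misfit to fit will be the decision rule. What remains is that C rose at least trivially in 75% of runs with a useless measure, so a rise without an interval or test is not evidence of improvement.

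Second, GEE software routinely prints a robust Wald test for each coefficient. A test of the added term is therefore unnamed rather than ruled out. That is fair, but a plan should say which result answers its question.

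Third, the latent profile analysis that defines the clusters is to draw on physician measures as well as patient and laboratory ones. If a measure helped define the outcome, a significance test of adding it is expected to reject and says little about usefulness. This stands too, and it is why the fix puts the size of the change beside the p-value.

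Fourth, a reader might infer that this comparison decides whether the new indicator is presented as sufficient without a physician measure, or that the three measures would be ranked by noise. No text makes the first link: the measure is called preliminary, and Aim 3 includes the patient survey in its tools without conditioning on this result. The second was not examined, since the simulations add one measure to one score.

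**Conclusion.** The point holds as a mismatch between question and tool. The question compares models; the only tool assigned to fit does not. On the assumptions above (alpha 0.05, ten groups, binary outcome, base model of the right shape), Hosmer-Lemeshow rejects a model lacking a strong predictor at about its nominal 5%, up to 8.2% with heavy clustering. In the independent-visit runs its p-value was about as likely to fall as to rise when the predictor was added. A patient-clustered test on the same data detects an odds ratio of 2 per SD in 98–100% of runs, and of 1.5 in 66–99% depending on clustering. The 98–100% detection at odds ratio 1.5 with independent visits is a likelihood-ratio result and should not be read as the power of the GEE analysis.

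The practical harm is moderate. C supplies comparative information but no stated way of judging the change. I read the physician measures as being added to the new scores; the text does not say so outright. If a measure were instead to replace the scores, the models would not be nested, and only the change in C and in Brier or log score would apply.

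**What to change.** Revise the Aim 2 Data Analysis paragraph as follows.

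1. State the base model: GEE logistic regression of cluster assignment on the new Type 1 and Type 2 scores. Add each physician measure in turn, and say how more than two clusters are handled.
2. Judge improvement by the change in C and the change in Brier or log score. Give each an interval from a bootstrap that resamples patients, not visits, and refits both models each time.
3. Report the patient-clustered robust Wald or score test of the added term beside these. Because physician measures may have helped form the clusters, say that the size of the change will be read with the p-value.
4. Use a calibration slope and plot for each model. If Hosmer-Lemeshow is kept, describe it as a calibration check of a single model and not as evidence that fit improved.

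The cost is a wording change and a little more analysis on the same 800 visits and the same models. No new data are needed.

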We are currently piloting two patient-reported outcomes (PRO) measures for Type 1 and 2 SLE: The Fibromyalgia Severity Score (FSS) allows patients to indicate areas of pain, extent of fatigue, waking unrefreshed, and cognitive symptoms. The FSS was designed to diagnose fibromyalgia, but we have found this scale clinically useful to efficiently measure the current extent of Type 2 SLE symptoms. The Systemic Lupus Activity Questionnaire (SLAQ) is a 24-symptom patient-reported measure of SLE activity. It partially correlates with the physician-reported Systemic Lupus Activity Measure. We have found the SLAQ clinically useful in highlighting important symptoms for patients, but the current scoring system combines Type 1 and 2 SLE activity, resulting in an assessment that is not clinically actionable.

The proposed research will build a brief preliminary PRO measure that combines features of the FSS and the SLAQ to indicate the current degree of Type 1 and Type 2 SLE activity, allowing for rapid assessment and appropriate treatment in practice.

The overall objective of this study is to develop a composite measure based on our conceptual model of Type 1 and 2 SLE to distinguish between these two symptom complexes, and then conduct a pilot implementation study of the measure within Duke Rheumatology. The central hypothesis is that Type 1 and 2 SLE are clinically distinct components of SLE that, once distinguished, will lead to improvements in the clinical management of SLE.

Methods:

Aim 1: Ensure the Type 1 and 2 SLE model matches the patient experience with lupus.

We will conduct a qualitative, descriptive study. For objective #1, we will conduct in-depth interviews. For objective #2, we will conduct cognitive interviews. In-depth interviews will be completed prior to cognitive interviews. Information learned in the in-depth interviews to develop patient-reported measures will be reviewed in the cognitive interviews.

In-depth interviews: During the in-depth interviews, participants will be asked to share their perspective on the experience with Type 1 and 2 SLE symptoms, treatments, and how their experience with lupus fits with the Type 1 and 2 SLE model. (See attachment for the question guide).

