Cognitive interviews: Cognitive interviews determine how individuals process and respond to survey questions that were modified based on information learned during the in-depth interviews (Tourangeau 1984; Willis 2013). For our research, we seek to will learn how participants interpret each question and fit each symptom of the SLAQ and FSS into the Type 1 and 2 SLE model.

During the cognitive interviews, participants will be asked to describe how they responded to each survey question, how the question distinguishes between Type 1 and 2 SLE symptoms, and if there are any symptoms that are not currently included on the survey. The questions asked during cognitive interviews will be dependent upon the results of the in-depth interviews. Therefore, a question guide will be submitted as an amendment to the IRB prior to starting interviews.

In-depth interviews and cognitive interviews: The in-depth and cognitive interviews will be conducted by a trained interviewer on the telephone or in-person. They will each last about 1 to 1.5 hours and will be audio-recorded with an encrypted recorder. If an individual wishes to not be audio-recorded, detailed

notes will be taken instead. Demographic information will also be collected (see attachment for demographic questionnaire).

As a standard practice used in qualitative research, changes may be made to the question guide and demographic questionnaire during study preparation, training, pre-testing, and data collection to improve phrasing, probes, or the flow of questions or to add related questions. If the changes are within the overall topic domains or related topics currently described within this protocol, the revised questionnaire(s) will not be submitted to the IRB. If the changes fall outside of the current domains or related topics, we will submit the revised questionnaire to the IRB for review before implementation.

Inclusion: Individuals are eligible to participate if they have an established diagnosis of SLE and are followed in the Duke Lupus Clinic. Participants will be selected based on the extent of their Type 1 and Type 2 symptoms. These classifications will be based patient- and physician-reported measures from the prior visit to the Duke Lupus Clinic. We will exclude patients with significant cognitive impairment as determined by the treating rheumatologist.

Sample size:

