In-depth interviews: We will conduct 12 to 15 interviews with individuals who experience higher Type 2 symptoms and 12-15 interviews with individuals who experience lower Type 2 symptoms. We chose these samples sizes because thematic saturation is typically reached around 12 interviews (Guest 2006). The interviewers will assess based on informational redundancy whether 3 additional interviews are needed.

Cognitive interviews: We will conduct at least two rounds of 10 cognitive interviews. Each round will include five participants who experience higher Type 2 symptoms and five participants who experience lower Type 2 symptoms. If further changes are necessary to the measures reviewed during the initial two rounds cognitive interviews, an additional six interviews will be conducted.

Participant selection and recruitment: We will purposefully select participants (Patton 2005) to identify the range of experiences. We will enroll a diverse study population with respect to 1) race (i.e., white and African American individuals) and 2) age (i.e., a range of ages, with an emphasis on recruiting young women). We will also stratified based on individuals' experience with higher versus lower Type 2 symptoms. These classifications will be based patient- and physician-reported measures from the prior visit to the Duke Lupus Clinic. High Type 1 symptoms will be defined as a SLEDAI score ≥ 6 (Gladman 2002). High Type 2 symptoms will be defined as a fibromyalgia severity score (widespread pain index + symptom severity index) ≥ 12 (Wolfe 2011).

Lupus Clinic is held each Wednesday in Duke South Clinic 1J. Prior to each weekly clinic, the patient list will be reviewed to identify potentially eligible patients. Eligibility will be determined based on information obtained from the medical record, as well as through a discussion with the individual's treating rheumatologist in the Duke Lupus Clinic. Prospective participants will be approached about the study during routine clinic visits at the Duke Lupus Clinic. The study will be introduced by the individual's Duke Rheumatologist.

Reimbursement: Participants will receive \$25 to reimburse them for their time participating in each interview.

Data Analysis: We will use descriptive statistics to summarize the demographic data and applied thematic analysis to analyze the qualitative data from the in-depth interviews and cognitive interviews.

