To impact patients, the Type 1 and 2 SLE model needs to be translated into an actionable tool. The overall goal of Aim 3 is to develop and test a set of electronic medical record (EMR)-based tools that enable rheumatologists to assess, discuss, and treat Type 1 and 2 SLE.

Tool Development. Over the past year, the physicians in the Duke Lupus Clinic have organically developed approaches to assessing and discussing Type 1 and 2 SLE with their patients. [name] will work with the providers in the Lupus Clinic to iteratively create SLE@Duke, a set of EMR-based tools to implement the Type 1 and 2 SLE model into clinical practice. Components will include a templated lupus note, dotphrases to assess and explain Type 1 and 2 SLE, the PRO survey, patient handouts, and suggested treatment plans. [name] will assess provider satisfaction quarterly at the Lupus Clinic Meeting as SLE@Duke tools are tested in clinic, making iterative changes based on their feedback.

Pilot Testing. This aim will pilot the SLE@Duke program with the Duke Rheumatologists outside of the Duke Lupus Clinic, where an estimated one-third of Duke Rheumatology's SLE patients are seen by 11 rheumatologists and 4 nurse practitioners. Non-Lupus Clinic providers and patients will complete surveys to assess satisfaction with visits and the treatment of SLE.

Interventions. SLE@Duke. The components of SLE@Duke will be made available in Epic for providers to assess and discuss patients' Type 1 and 2 SLE activity at each clinic visit. Physician & Clinic Training will include Rheumatology Division Grand Rounds and in-person Academic Detailing sessions in each of the clinics. Accompanied by a Duke Lupus Clinic provider, [name] will make frequent visits to the rheumatology clinics at 1J, Brier Creek, and South Durham to introduce the surveys, educate the nursing staff and providers on Type 1 and 2 SLE, and troubleshoot any issues that arise. The goal of these visits will be to introduce SLE@Duke, as well as solicit feedback on how to improve the tool.

Outcomes & Evaluation. We will use the RE-AIM framework to guide our collection of comprehensive information about the reach, effectiveness, adoption, implementation, and maintenance of SLE@Duke (Table 1)²⁵.

Table 1: RE-AIM Framework for Implementation Assessment

Provider-Level Outcomes	Patient-Level Outcomes
REACH: participant characteristics; differences between participants & non-participants	

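### Aim 1 tests whether the model matches patient experience only in the clinic where physicians already discuss it, and the described plan does not record or use prior exposure to the model

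*Combined protocol and SAP*

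**What the plan says.** Aim 1, Inclusion limits the interviews to one clinic: "Individuals are eligible to participate if they have an established diagnosis of SLE and are followed in the Duke Lupus Clinic". Higher or lower Type 2 symptoms are classified from "measures from the prior visit to the Duke Lupus Clinic", so every participant has been seen there at least once before. Under Participant selection and recruitment, "Prospective participants will be approached about the study during routine clinic visits at the Duke Lupus Clinic". The first mention of the research comes from the treating doctor, since that section adds: "The study will be introduced by the individual's Duke Rheumatologist".

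In the in-depth interviews participants are asked, among other things, "how their experience with lupus fits with the Type 1 and 2 SLE model". In the cognitive interviews they are asked to place SLAQ and FSS symptoms within the model, and the interviewer's debriefing form records each symptom's Type 1 or Type 2 assignment.

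The fact that bears on all this appears later. Under Aim 3, Tool Development, the plan reports that this clinic's doctors had, during the preceding year, "organically developed approaches to assessing and discussing Type 1 and 2 SLE with their patients".

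**The concern.** Someone to whom a physician has explained the model can answer a question about fit, or about whether fatigue is Type 1 or Type 2, from memory of that explanation. Someone who has not met the model must answer from experience. Only the second kind of answer is independent evidence that the model describes what patients go through. If the two kinds are pooled without a marker, a reader of the Aim 1 report cannot tell how much of the agreement is independent.

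Two planned procedures could be affected. Code frequencies are used to find the most prominent themes, and redundancy of information decides whether three more interviews are needed in a symptom group. Vocabulary shared through one clinic could raise the first and bring the second forward.

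The result also travels. In Aim 2, qualitative information from the interviews is one of three inputs to the revised SLAQ and its Type 1 and Type 2 scores, alongside SLAQ differences by cluster and clinical expertise. If interview answers partly echo clinicians, the qualitative and clinical inputs are less separate than they look.

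**Working it through.** No error rate or sample-size formula applies, because Aim 1 is qualitative and descriptive. The check is a count of the planned interviews and a comparison of what the sections say.

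**Count (Aim 1, Sample size)**
- In-depth interviews: 12 to 15 with higher and 12 to 15 with lower Type 2 symptoms, so 12 + 12 = 24 to 15 + 15 = 30.
- Cognitive interviews: two rounds of 10, so 2 × 10 = 20; with the optional six, 20 + 6 = 26.
- Total: 24 + 20 = 44 to 30 + 26 = 56 interviews. These are interviews, not necessarily different people.
- From the Duke Lupus Clinic: all of them. From elsewhere in Duke Rheumatology: none.

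**Opportunity for exposure.** Each participant has had an earlier visit to the clinic, and that clinic's physicians have been developing ways to discuss the model for about a year. The text does not say how many patients have had that discussion. Among the 24 to 30 in-depth interviews, the number of unexposed patients could be anything from none to all.

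**Does the described plan use exposure?**
- Sampling: diversity is sought on race and age, and stratification is by Type 2 symptom level. Exposure is not a criterion.
- Data collection: a demographic questionnaire and the interview guides. Their content is not in the text available, and the text mentions no exposure item.
- Analysis: structural codes, thematic codes, code frequencies and debriefing summaries. No comparison by exposure is described.

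**Which answers are sensitive?** Model fit (in-depth) and symptom assignment (cognitive) refer to the model itself, so a prior explanation can shape them directly. Questions on symptoms, on treatments and on symptoms missing from the survey can be answered without knowing the model.

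**Is exposure measurable?** Yes. Table 1, under Effectiveness and Adoption, already plans to learn from the Aim 3 patient survey whether the model was discussed at the visit. Aim 1 has no counterpart in the text.

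**Are there patients outside this clinic?** Yes. Aim 3 puts about one-third of the division's SLE patients outside the Lupus Clinic, about 260 over six months. They are eligible for Aim 3 but not for Aim 1.

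**The case against.** A reader might infer that every interviewee has been taught the model, that taught agreement can never be separated from real fit, and that the Aim 1 conclusion is therefore biased. The documents do not support that, for these reasons.

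- Tool Development describes approaches that grew up informally. It does not say that patients were taught systematically, or how many were. Exposure may well vary between participants.
- The in-depth guide and the demographic questionnaire are attachments that are not shown, and the cognitive guide was to follow by amendment. Any of them might ask about prior explanation. The plan also lets related questions and probes be added during data collection, and verbatim transcripts could be coded for such accounts.
- The Purpose of the Study includes modifying the model in the light of patients' experiences, so Aim 1 is not only a test of agreement.
- No proportion endorsing the model is planned, so a bias expressed in percentage points has no target here.
- The Aim 2 scores have two other inputs and are checked against cluster assignment in 800 visits. Aim 1 agreement does not settle the scoring.

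All of this stands, and it limits the point to a possible influence on two kinds of answer. It does not remove the gap. Varying exposure helps only if it is recorded, and even a guide that asks about it would leave the described analysis without a step that uses the answer. The Aim 2 check compares scores with clusters; it does not show whether interviewees' symptom assignments were their own.

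A fixed quota of unexposed patients, or a rule that a theme counts only if unexposed patients also voice it, would go too far. A few such patients per stratum fall well short of the roughly 12 interviews on which the plan bases saturation, so genuine themes could be lost. Patients wholly new to the clinic would also lack the prior visit that the classification needs.

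**Conclusion.** The point holds in a limited form. The described Aim 1 plan draws all 44 to 56 interviews from the one clinic known to be discussing the model, and it neither records nor analyses prior exposure. Model-fit and symptom-assignment answers may partly reflect what a physician said. By how much cannot be stated, because the exposed share is not given.

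This rests on two assumptions: that discussing the model with patients leaves at least some of them knowing its terms, and that the unseen guides and questionnaire do not already capture this. If they do, only the reporting and the wording of the conclusion remain to be settled. The interviews keep their value for describing symptoms and treatments. This is an inexpensive improvement that changes what Aim 1 can conclude; it is not a flaw that invalidates the aim.

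**What to change.** In both the in-depth and the cognitive interviews:

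1. Ask about symptom experience before presenting the model.
2. Record whether, and roughly when, a provider has explained the Type 1 and 2 model to the participant.
3. Report model-fit and symptom-assignment themes by prior exposure, with the number of interviews in each group.
4. State in the plan that the conclusion that the model matches patient experience will be qualified if few or no unexposed patients were interviewed.
5. Where feasible, include some unexposed patients within the planned 24 to 30 in-depth interviews, with no fixed quota and no rule that a theme must appear among them.

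The cost is one added question, one more column in the theme tables, and no extra interviews. The cognitive guide was still to be submitted, so the question can go in then. For the in-depth guide, the plan already allows related questions to be added. The downside is that the exposure groups will be small and can only be described. Someone who has not met the model will also have it explained during the interview, so the contrast will not be clean, which is why symptom experience should be asked about first. Recruiting from outside the Lupus Clinic would mean widening Aim 1 eligibility and finding another basis for the symptom classification, so it is not asked for here.
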